5.1. Identification numbers

Each subject who has signed a written IRB/Ethics Committee approved Informed Consent Form will receive a unique subject ID number. The number will have 6 digits. The first two numbers will be the country code, the next two digits will define the center and the last two digits will be consecutive screened subjects in this center.

After all baseline medical data is recorded and the wound is documented at the 2 week baseline/randomization visit, the subject's number will become the subject identification number (Subject ID) for the remainder for the study. The investigator will not know to which treatment arm the subject is allocated throughout the trial.

5.2. Allocation concealment

Randomization will be coordinated by a central randomization center. Neither investigator nor subject will know their randomization allocation or can influence their allocation (=allocation concealment).

6. TRIAL TREATMENT MODALITIES

6.1. Trial Treatment

The TWO₂ group will receive topical oxygen as an adjunctive treatment to standard of care treatment. The TWO₂ treatment consists of the Topical Wound Oxygen therapy system (AOTI Ltd.) as well as an oxygen concentrator. Oxygen will be delivered to the device at a flow rate of at least 10 liters/ minute.

After connecting the TWO₂ Single patient-use leg chamber to the controller and concentrator, the controller initiates 4 phases of the treatment:

Phase 1:

The outer leg chamber is inflated. The limb with the ulcer can then be placed into the chamber.

Phase 2:

The integrated cuff is inflated to seal the inside of the chamber against the limb.

Phase 3:

The therapy phase: Cyclical pressurized oxygen is delivered to the limb inside the chamber.

Phase 4:

The cuff and outer leg chamber is deflated and removed from subject's limb.

This setup delivers cyclical pressurized oxygen to the wound site within a sealed and humidified environment.

The affected limb will be placed in the chamber for 90 minutes daily, 5 days a week, for a period of up to 12 weeks (plus an additional 2 visits, 2 weeks apart to confirm wound closure for index ulcers closing at week 9 or later) or until full closure of the wound, whichever is sooner.

All treatments can be done with or without removing the dressings.

The picture below shows the TWO₂ Single patient-use leg chamber and the controller.

6.2. Control Treatment

The control treatment will look and act exactly like the TWO2 treatment. The only difference is that the controller has technical modifications.

In phase 3, the control therapy will not supply oxygen or pressure to the affected limb during the treatment but mimics the therapy on the display with pressure values that go up and down.

All other phases of device operation are identical.

6.3. Standard Care Treatment

Subjects in both groups will receive the same standard care regime that includes sharps debridement of all callus/necrotic tissue, AMWT and off-loading, where it is required. In a multi-center trial the value of study site consistency in standard care regimens within a trial cannot be over-emphasized because of the profound effects these procedures have on clinical outcome for chronic wounds.²³ Consistency in standard care regimens is important for minimizing variability and allowing assessment of treatment effect. Every attempt will be made to minimize deviations from the procedures described in the protocol and subject compliance recorded in CRFs.

In order to minimize variability in standard of care between sites:

- All centers will perform a standardized training before the trial
- All centers will be monitored closely by a study site monitor and the study director

6.3.1. Debridement

Adequate debridement is key for wound healing in diabetic ulcers. All wounds will receive baseline sharps debridement of all callus/necrotic tissue and additional debridement as needed throughout the trial. Debridement will be performed where it is determined to be clinically necessary by the PI/SubI.

Any surgical debridement has to be documented on CRFs, reported as an adverse event and will be included in analysis of product safety and efficacy.

Standardized debridement will be part of the Investigators training. To ensure the same standard of debridement/wound preparation in all centers, photographs of all subjects will be evaluated by a central assessor.

Enzymatic debridement products, like other concomitant topical products, can confound results in topical wound-treatment product trials and therefore must be prohibited.

6.3.2. **Off-Loading**

Excessive pressure on the sole of the foot is one of the key factors in the pathogenesis of neuropathic plantar ulcers. Consequently pressure relief is of fundamental importance in the treatment of the diabetic foot ulcer³⁰ and has been intensively proven in well designed randomized clinical trials.^{24,26,31,32}

Therefore all subjects in the present study will be provided with an off-loading device (for weight bearing wounds) from Salvatelli srl, Italy (Piaggesi study):

During the weekly wound assessment, subjects will be educated about the importance of the off-loading (where it is required).

6.3.3. Dressing Changes and Wound Dressing

Dressing changes will be performed a minimum of once a week according to the Investigators recommendation and consist of the following procedures:

1. Dressing removal
2. Cleansing with saline
3. Application of new dressing

At each dressing change the wound will be cleansed with saline.

Antiseptic substances like Octenisept®, Prontosan®, or similar products CANNOT be used in this trial.

All wound dressings will be from Convatec/Kendall. The wound dressings will be limited to the following:

Primary Dressing

Kendall Foam Dressing,

Wound filling dry wounds

Curafil™* Gel Wound Dressing 3 Ounce Tube

Secondary Dressing

Non-sterile Kerlix Rolls

Surgical Tape

Generic surgical tape one roll

Saline

Generic sterile saline 0.9%

The wound dressings selected by the Investigator for each subject, will be used in accordance with the manufacturer's guidelines and institutional protocols and healthcare professional's judgment.

The number of dressing changes will be documented in the CRFs.

Dressing changes can be performed by the subject, caregiver or healthcare professional (such as a home health nurse or aide).

6.3.4. *Monitoring and treatment of wound infection*

Infection will be assessed clinically via symptoms and signs including purulent drainage, erythema, warmth, exudation, odor, pain, fever, and leukocytosis as well as wound size and time to wound healing. In patients with diabetes, fever, pain, and leukocytosis may be absent.³⁷⁻⁴¹

Mild and moderate infections can be included into the study. No local antimicrobial treatments are allowed in the study. Systemic antibiotic treatment of infection will be prescribed according to local standards (refer to section 3.3.4.).

An infection that needs hospitalization is regarded as a severe adverse event or device effect and the subject will be suspended from the study for up to 4 weeks, up to 2 times, and may rejoin the study on resolution and compliance with other inclusion criteria.

6.3.5. *Education*

Subjects will be educated during each study visit about the importance of maintaining normal blood glucose levels and encouraged on continued appropriate diabetes management including diet and medications to achieve or maintain a stable glycemic state. Subjects will also be educated on how to care for their feet.

Routine laboratory testing of blood glucose or HbA1c is included in this trial and will be drawn at the screening visit and at the end of the treatment period.

Comorbidities are documented but no special treatment of comorbidities is part of this trial.

6.4. *Treatment modalities not allowed in the study*

Other adjunctive or alternative treatments, such as; Hyperbaric oxygen therapy (HBO), Vacuum assisted closure (VAC), Heat therapy, Laser therapy, Mechanical constant tension, Larval/maggot therapy (Biodebridement), Electrical stimulation (ESTR), Artificial skin (Dermagraft) are not allowed during this study.

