4.3. Removal of Subjects from Therapy or Assessment

Subjects may discontinue study treatment and withdraw from the study at any time. The reasons for withdrawal may include the subject withdrawing their consent to participate in the study, or Investigator may decide to withdraw the subject from the study because of Adverse Events and Device Effects (ADE) or subject non-compliance.

Where subjects are removed from study treatment (TWO2 therapy or Control therapy) for other than non-compliance and continue to provide consent to participate, may continue with study visits to assess for primary and secondary endpoints. This may include:

- 12 week final treatment visit
- 12 week follow up
- 38 week follow up

If treatment is terminated and no follow up visits are anticipated, the final evaluation will be performed as completely as possible. In addition, any comments (spontaneous or elicited) or complaints made by the subject and the reason for termination will be recorded in the CRF and the subject's medical records.

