The End of Trial Visit should occur on or as close as possible to treatment week 12. Though encouraged to do so in all cases, some subjects may still decline to attend this visit, in which case this will be recorded in the CRF (along with any reasons if given). Subjects who are withdrawn from the treatment will be asked if they consent to be followed up after withdrawal to determine whether their ulcer heals within the 12 weeks from randomization.

In addition, a follow-up after 12 weeks and/or 38 weeks will be undertaken wherever possible in those that were withdrawn to confirm whether they healed according to intention-to-treat (ITT).

8.2.7 *Procedures for confirmation of wound closure*

Subjects with index ulcers that are observed to close will be followed for 4 weeks to confirm wound closure. During this period, subjects will continue to receive treatment and dressing changes and wear the standard off-loading device. If wound closure occurs within the 11th week, treatment will continue for an additional 2 weeks to confirm closure (up to a maximum of 14 weeks of treatment).

The wound closure confirmation assessment will be done at confirmation visits 2 weeks after closure.

- 1) Verify Informed Consent
- 2) Record adverse events/device effects
- 3) Record changes in concomitant medication
- 4) Quality of Life Assessment using CWIS (If week 12 on treatment or last visit before follow up)
- 5) Collect diary card/Compliance assessment (treatment/dressings)
- 6) Confirm wound closure for past week
- 7) Pain Assessment using the Visual Numerical Rating Scale
- 8) Wound History: time of wound closure
- 9) Digital Photograph of the closed index ulcer
- 10) Education on diabetes management and foot care/off-loading boot/CROW boot
- 11) Dispense study dressings (confirmation visit 1 only) /dressings (if indicated confirmation visit 2) and diary card (confirmation visit 1 only)
- 12) EQ-5D (if week 4, 8 or 12 on treatment or last visit before follow up)
- 13) Blood sample taken to obtain values for (if at week 12 from randomization or at last closure visit if before):
 - Electrolytes
 - Creatinine
 - HbA1c, blood glucose
 - WBC
 - Albumin and pre-albumin (where available)
 - CBC
 - C-reactive protein

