9.2 General Statistical Methods

Analysis Populations

Two analysis populations will be evaluated: Intent To Treat (ITT) and Per Protocol (PP). The ITT population will be considered the primary population of interest and will include all subjects who were randomized to study treatment. The PP population will include all subjects who were randomized to study treatment and had no significant protocol violations that might affect the outcome of treatment.

All participants will be followed up to the primary end point (12 weeks) irrespective of whether they were on active treatment. Participants that withdraw from treatment continue to be followed up to the 12 week end-point. Participants that die, undergo amputation or who are lost to follow up will be considered as treatment failures.

Continuous demographic variables (age, ulcer duration, etc.) will be summarized for the study population as descriptive statistics (number, mean, median, SD, minimum and maximum value), and by randomized groups. No formal inferential statistical testing will take place of baseline values in relation to randomized groups.

Categorical demographic variables, such as gender, will be summarized as a proportion of the intention-to-treat population.

All analyses will be undertaken using the STATA 11 statistical package.

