Fisher's Exact Test will be used. An approximate 95% confidence interval for the difference between treatment groups in terms of amputation rate will be estimated using the normal approximation interval.

9.4.5 *Safety and Tolerability*

Safety and tolerability data will be presented in summary form and in detailed data listings. No significance testing will be applied to these data.

9.5 *Missing and Spurious Data*

No procedures are planned for the imputation of missing data. Subjects with missing data will be omitted from the relevant analyses.

If main outcomes are missing every attempt should be made to discover why and rectify wherever possible. If it is still not possible to discover the outcomes then the reason for this must be recorded e.g. death, refusal, incapacity.

For the health economic analysis it is standard procedure to impute missing data where necessary in order that an appropriate estimate can be given of the total costs of care.

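### Section 6.3.4 suspends subjects hospitalised for infection from the study, not from treatment, and so conflicts with the week-12 follow-up rule in 9.2

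*Combined protocol and SAP*

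**What the plan says.** Section 6.3.4 (Monitoring and treatment of wound infection) covers infection that needs hospitalisation. The subject is "suspended from the study for up to 4 weeks, up to 2 times, and may rejoin the study on resolution and compliance with" the other inclusion criteria.

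Section 9.2 sets a different rule. On the analysis set: "The ITT population will be considered the primary population of interest and will include all subjects who were randomized to study treatment". On follow-up: "All participants will be followed up to the primary end point (12 weeks) irrespective of whether they were on active treatment". On coding: "Participants that die, undergo amputation or who are lost to follow up will be considered as treatment failures".

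Section 9.5 plans no imputation and adds: "Subjects with missing data will be omitted from the relevant analyses".

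Four other places bear on the same subjects:

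- **8.2.12** covers a hospital stay for the ulcer or another condition. Up to 4 weeks, the aim is to carry on with trial treatment after discharge, and no eligibility re-check is mentioned.
- **3.1** says that subjects withdrawn from the treatment phase will be asked back for the final week-12 visit.
- **4.3** says that subjects taken off treatment for reasons other than non-compliance "may continue with study visits to assess for primary and secondary endpoints".
- **8.2.6** says that withdrawn subjects will be asked to consent to follow-up of healing within 12 weeks of randomisation.

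**The concern.** A site that follows 6.3.4 to the letter would stop seeing a randomised subject, and would readmit that subject only after a check against entry criteria. A site that follows 9.2 would keep assessing the same subject to week 12. It cannot do both.

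The subjects affected are not a random subset. They are picked out by a serious infection after randomisation, which is linked to poor healing and could differ between arms. The event is foreseeable: infected ulcers are eligible, and 3.3.3 lists severe infection needing hospitalisation as a safety endpoint.

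The primary endpoint depends on attendance. Closure is checked weekly and needs confirmation at two visits two weeks apart. Two suspensions of 4 weeks could remove 2 × 4 = 8 of the 12 weeks. Section 9.1 adds no patients for losses because every patient is expected to have a 12-week outcome.

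**Working it through.** **1. Can the re-check exclude anyone?** Two inclusion criteria in 4.1 are fixed in the past: size at the start of run-in and reduction during run-in. Others can change after randomisation: University of Texas grade 1 or 2, perfusion, and no revascularisation within 30 days. Ulcer duration of at most 1 year can lapse with time alone. So, read literally, the condition can keep a subject out.

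**2. How would a subject kept out be coded?** Section 9.2 names three failure events: death, amputation and loss to follow-up. Section 8.2.12 reserves loss to follow-up for subjects not recovered after at least four attempts. A suspended subject who is still in contact meets none of these. If no week-12 status exists, 9.2 read by analogy suggests failure, while 9.5 says omit.

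**3. Does the clock stop?** Section 6.3.4 does not say. The 54-week maximum in 3.1 equals 2 (run-in) + 14 (longest treatment, 8.2.7) + 12 + 26 (follow-up). That leaves no room for 8 added weeks, which favours counting from randomisation, as 8.2.6 does.

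**4. The plan's own sample size.** Inputs from 9.1: 43% v 64%, 80% power, no continuity correction; two-sided testing is assumed. The formula is n = [z_α √(2p̄(1−p̄)) + z_β √(p₁q₁ + p₂q₂)]² / (p₂−p₁)², with p̄ = 0.535.

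- Level 0.05: (1.960 × 0.7054 + 0.8416 × 0.6896)² / 0.0441 = 87.4, so 88 per arm.
- Level 0.022: (2.290 × 0.7054 + 0.8416 × 0.6896)² / 0.0441 = 109.3, so 110 per arm.

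Both figures reproduce. Single-look power with 110 per arm at 0.022 is 80.3%.

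**5. What the coding choice is worth.** The shares below are assumptions. Let p be the arm's rate, s the share with no week-12 outcome, and h·p the closure rate those subjects would have had, with h from 0 to 1.

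- Failure coding: p − s·h·p, on 110 per arm.
- Omission: (p − s·h·p)/(1 − s), on 110(1 − s) per arm.

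Example with 5% in each arm and h = 1: failure coding gives 0.64 × 0.95 − 0.43 × 0.95 = 0.608 − 0.4085 = 19.95 points, and omission gives 21.0.

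| s, control / TWO2 | Failure: difference, h = 0 to 1 | Omission: difference, h = 0 to 1 | Omission minus failure |
|---|---|---|---|
| 2% / 2% | 21.0 to 20.58 | 21.43 to 21.0 | 0.43 to 0.42 |
| 5% / 5% | 21.0 to 19.95 | 22.11 to 21.0 | 1.11 to 1.05 |
| 10% / 10% | 21.0 to 18.9 | 23.33 to 21.0 | 2.33 to 2.10 |
| 5% / 10% | 21.0 to 16.75 | 25.85 to 21.0 | 4.85 to 4.25 |
| 10% / 5% | 21.0 to 22.1 | 19.59 to 21.0 | −1.41 to −1.10 |

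**6. Power.** At h = 1 and 5% in each arm, single-look power is 75.3% with failure coding and 77.9% with omission. The trial has three looks (73, 146 and 220 subjects, 0.022 each). Simulated power over all three is about 84% with no loss. With failure coding at h = 1 it is about 83%, 80% and 76% at 2%, 5% and 10% per arm. At h = 0 failure coding costs nothing, because the rates stay at 43% and 64% on 110 per arm.

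**The case against.** The strongest reply is that this is a loose phrase whose meaning the rest of the protocol settles. Section 6.3.4 sits in the chapter on treatment modalities. Section 8.2.12 treats the same kind of hospital stay, with the same 4-week limit, as a break in treatment. The follow-up rule in 9.2 is mandatory. If even withdrawn subjects are asked back at week 12 (3.1, 8.2.6), a suspended one would hardly be left out. The qualifier in 8.2.6 that follow-up happens where it can is attached to the 12- and 38-week visits, not to healing status at week 12. Few sites would bar a returning subject because the ulcer had passed its first year during the trial. Section 9.1 also refers to 9.2 for losses, which favours failure coding over omission.

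Most of this stands, and it makes a treatment pause the probable intent. It does not remove the conflict. No section says that 6.3.4 means treatment only, so sites have two rules for one event, and 4.3 is permissive. The pointer in 9.1 does not override 9.5 or add suspended subjects to the failure list.

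A reader might infer that the plan removes these subjects from the intention-to-treat set through an eligibility filter. It does not: 9.2 keeps every randomised subject in that set. A reader might also take the shifts in the table as the effect of 6.3.4. They measure the general tension between 9.2 and 9.5, which applies to any subject without a week-12 outcome. Section 6.3.4 only adds one route into it.

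**Conclusion.** The concern holds as a conflict of wording with a practical consequence. Taken literally, 6.3.4 stops outcome collection in subjects selected by a post-randomisation event linked to poor healing, against 9.2, 8.2.12 and 3.1. The likely harm is missing closure assessments and an unsettled coding choice. The analysis set and the sample size of 220 are not affected.

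No effect size can be given for 6.3.4, because the documents state neither how often suspension would occur nor how many subjects would fail to return. At small, equal non-return the coding choice matters little: about 0.4 points at 2% per arm and 1.1 at 5%. It matters more if non-return is unequal, at 4.3 to 4.9 points for 5% control and 10% TWO2. Nothing in the documents shows that rates of this size, or such an imbalance, are to be expected. The documents do not support a conclusion that the trial is underpowered on this account: over three looks, an assumed 5% loss per arm at the unfavourable end still leaves about 80%.

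**What to change.** **Section 6.3.4.** Write *suspended from study treatment*. State that the subject stays in the study, keeps visits where feasible, and has the week-12 assessment counted from randomisation. State that any re-check of criteria decides only whether the device is resumed.

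**Sections 9.2 and 9.5.** State that, for the primary intention-to-treat endpoint, any randomised subject without a week-12 outcome counts as a treatment failure, and that this overrides the omission rule in 9.5.

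**Cost.** This is amendment wording only, with no extra patients or scheduled visits. Failure coding does lose power if non-returners would have healed (the three-look figures under working). It is also not neutral if non-return differs by arm: at h = 1 the 21-point difference becomes 16.75 at 5% control and 10% TWO2, and 22.1 with the shares reversed. The first change limits both effects, because subjects kept in follow-up should seldom lack a week-12 status. The rule should be settled before the first interim look, so that the choice cannot depend on results.

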7. ASSESSED VARIABLES

7.1. Efficacy Assessment

7.1.1. Primary Efficacy Assessment

The primary endpoint is the “Incidence of complete wound closure within 12 weeks”.

Only one ulcer (the index ulcer) will be assessed per subject. In subjects with multiple ulcers, this will be the largest ulcer present fulfilling all other inclusion criteria.

Closure is defined as skin re-epithelialization without drainage or dressing requirements which is confirmed at 2 consecutive trial visits 2 weeks apart.²³

Wound closure checks will be performed weekly. The closure of the wound is a clinical judgment by the investigator. A digital picture reviewed by the central assessor will also provide evidence of wound closure.

Ulcers will be measured by the central assessor. A deidentified digital photograph of the ulcer will be taken with and transmitted by the study sites using a wifi/wireless enabled tablet device. The ulcer's surface area, circumference, maximum and minimum diameters will be recorded at baseline assessment of the subject.

